5.1.1.1 Sample collection

Blood will be collected in 2 mL K₂EDTA tubes (purple top) at the times defined in Section **5.2**. Samples should be inverted 8 to 10 times after collection. Store on wet ice or at 4°C. Processing within 60 minutes of blood collection is highly preferred, but not required as samples are stable at 4°C for up to 24 hours.

5.1.1.2 Sample processing

Samples will be processed in the Clinical Pharmacology Program.

Please e-mail [contact] at least 24 hours before transporting samples (the Friday before is preferred).

For sample pickup, page [name].

For immediate help, call [contact] (main blood processing core number) or, if no answer, [contact] (main clinical pharmacology lab number).

For questions regarding sample processing, contact [contact].

Upon arrival in the CPP the following procedures should be followed:

- 1. Store on wet ice until centrifugation.
- 2. Centrifuge 1500xg for 10 minutes at 4°C within 60 minutes of blood collection.
- 3. Transfer plasma specimen to 2mL cryovials and store at -70°C.

The analyses will be performed retrospectively in batched samples or at the end of the trial.

5.1.1.4 Sample storage

Samples will be stored in the CPP until shipment to the Leidos Biomedical Inc. Lab in Frederick.

5.1.2 Assessment of LMB-100 anti-drug antibodies (ADAs)

5.1.2.1 Sample Collection

Samples will be collected before the first dose of LMB-100 during each cycle as per Section 5.2.

Draw 2mL into K₂EDTA tube (purple top). Samples should be inverted 8 to 10 times after collection. Store on wet ice or at 4°C. Processing within 60 minutes of blood collection is highly preferred.

5.1.2.2 Sample Processing, Shipping and Storing

Samples will be processed in the Clinical Pharmacology Program as described in Section **5.1.1.2** and autoantibody levels will be retrospectively assessed. Samples will be shipped as described in Section **5.1.1.3** and stored as described in Section **5.1.1.4**.

5.1.3 Cytokines and circulating endothelial cells (CECs) for identification of a mechanism for PE-mediated capillary leak syndrome (CLS)

PE-based RITs cause dose-limiting CLS. At low doses CLS manifests as mild and transient weight gain, hypoalbuminemia, and peripheral or facial edema. At higher doses it can cause life-threatening cardiopulmonary compromise. Previous studies in rats have indicated that pathological changes indicative of CLS onset occur within just two hours of toxin administration and even when the PE fragment lacks a targeting domain (36). *In vitro* studies with cultured endothelial cells have demonstrated that super-physiologic doses of PE-based RITs cannot induce endothelial cell toxicity unless the cells express the RIT target (37). Together these data suggest the hypothesis that **PE-based RITs cause CLS by triggering release of vasoactive cytokines by specific immune cells rather than through direct damage to endothelial cells. To test this hypothesis, we will collect additional blood from participants. Levels of a panel of cytokines known to affect the vasculature will be assessed. Change in cytokine levels from baseline will be compared.**

Abbreviated Title: LMB100 + *tofacitinib in PDA Version Date:* 08/19/20

In addition, circulating endothelial progenitor cells (CEP) and mature circulating endothelial cells (CEC) will be collected to assess endothelial cell dynamics (see Section **5.2** for specific time points). These cells will be assessed by multiparameter flow cytometry. Cells will be analyzed for forward and side scatter, and cells expressing hematopoietic markers will be excluded. Endothelial cells will be identified using co-expression of markers, such as CD31 and CD146 for CEC, and CD31 and CD133 for CEP. The cell populations will also be analyzed for viability using scatter profiles and a vital stain, such as Hoechst 33258. Percentages of stained cells will be determined and compared with appropriate negative controls. Multiparameter flow cytometric analysis will be performed with a Miltenyi Quant equipped with FlowJo software, using a minimum of 100,000 events per analysis.

5.1.3.1 Specimen collection- cytokine analysis

Plasma and serum will be collected from participants on the days and time points shown in Sections **5.2**.

Draw 2mL into K₂EDTA tube (purple top). Samples should be inverted 8 to 10 times after collection. Store on wet ice or at 4°C. Samples must be processed within 120 minutes of blood collection due to instability of some analytes.

Draw 2mL into SST tube (red top).

5.1.3.2 Sample processing- cytokine analysis

Samples will be processed in the Clinical Pharmacology Program as described in Section 5.1.1.2.

Upon arrival in the CPP, each plasma sample (K₂EDTA tube) should be processed in the following manner:

- 1. Store on wet ice until centrifugation.
- 2. Centrifuge 1500xg for 10 minutes at 4°C within 60 minutes of blood collection.
- 3. Immediately transfer plasma specimen (maintaining samples at 4°C throughout handling process) to 2mL cryovials and store at -70°C.

Upon arrival in the CPP, each serum sample (SST tube) should be processed in the following manner:

- 1. Store at room temperature for 15-30 minutes to allow blood to clot
- 2. Centrifuge at 1500xg for 10 minutes at 4°C to remove clot
- 3. Immediately transfer serum specimen (maintaining samples at 4°C throughout handling process) to 2mL cryovials and store at -70°C.

5.1.3.3 Sample Storage- cytokine analysis

Samples will be stored in the CPP. Deidentified samples will be transferred to the [name] laboratory for analysis within 12 months of freezing.

5.1.3.4 Sample Collection- CECs

Draw blood into one 8-cc CPT citrate (BD) tube as specified in Section 5.2

5.1.4.1 Specimen collection, preparation and storage

Tumor biopsy specimens will be obtained when feasible with patient consent. Specimens will be processed and stored by NCI Laboratory of pathology and presence of tumor confirmed.

5.1.5 Retrospective Analysis of Mesothelin Expression in tumor tissue

IHC analysis will be performed by the Laboratory of Pathology at NCI to determine mesothelin expression within the tumor at any time after study enrollment. Leftover tissue from archival specimens or tumor biopsies obtained at screening will be used for analysis. Specimens will be used to correlate treatment with response with mesothelin expression in an exploratory analysis.

5.1.6 Peripheral blood immune gene expression

Peripheral blood mononuclear cells (PBMC) will be assessed by the [name] Lab using multiparameter flow cytometry for immune subsets including but not necessarily limited to CD8+ T-cells, CD4+Foxp3- T-cells, Tregs, Th1, Th2 and Th17+ CD4+ T-cells, monocyte subsets, MDSC subsets. Assessment will include functional markers, i.e. PD-1, Tim-3, CTLA-4, PD-L1, HLA-DR and/or CD40.

Peripheral blood immune gene expression will be evaluated by the [name] Lab using the NanoString nCounter® platform (NanoString Technologies, Seattle, WA). Collect peripheral whole blood in a PAXgene Blood RNA tube (PreAnalytix; 2.5 cc peripheral blood per tube) per the manufacturer's instructions. After the whole blood is drawn, the tube should be inverted several times and placed at room temperature. RNA will be isolated using the PAXgene Blood RNA Kit according to the manufacturer's instructions. Peripheral immune gene expression will be evaluated using the PanCancer Immune Profiling codeset of 730 immune genes and 40 control genes at baseline and post-therapy by the [name] Lab to look for correlates of clinical response with innate or adaptive immunity.

5.1.6.1 Sample Collection

Draw blood into one 8-cc CPT citrate (BD) tube at (1) baseline, just prior to beginning therapy, (2) cycle 1 following end of last infusion as specified in Section 5.2, and (3) cycle 2 day 1, prior

Abbreviated Title: LMB100 + *tofacitinib in PDA Version Date:* 08/19/20

to therapy. Draw blood into two one 2.5 ml PAXgene RNA tube at (1) baseline, just prior to beginning therapy, and (2) cycle 2 day 1, prior to therapy.

5.2 SAMPLE COLLECTION SCHEDULE

Cycle	Day	LMB- 100 PKs 5.1.1	ADA 5.1.2	Plasma & Serum Cytokines 5.1.3	CECs 5.1.3	Immune Subsets 5.1.6	Immune gene expression 5.1.6	Tumor Sample 5.1.4, 5.1.5
		2 mL K ₂ EDTA tube	2 mL K ₂ EDTA tube	2 mL K ₂ EDTA and SST tubes		CPT citrate tubes	2.5 mL PAX gene RNA tube	N/A
Screening								X ^a
	1 ^b		Pre- tofacitinib	Pre- tofacitinib		Pre- tofacitinib	Pre- tofacitinib	X ⁰
1	4	Pre-, EOI, then 1, 2, 4, 8-10, 12-16 hrs post- LMB-100	Pre-dose LMB- 100°	Pre-dose, EOI, 4hrs post- LMB-100	Pre-dose LMB-100	Pre-dose LMB-100		
	8	Pre-, EOI LMB-100						
	9			Х	Х	Х	Х	
	3		X ^c					
≥2	4	Pre-, EOI LMB-100 C3 only : 1, 2, 4, 8- 10, 12-16 hrs post- LMB-100		pre-LMB- 100	C2 only : pre- LMB-100	C2 only : pre- LMB-100		
	8	Pre-, EOI LMB-100		EOI LMB-100				X ^d
Treatment Extension	4	Pre-, EOI LMB-100	pre-LMB- 100					
At time of Progression			Х	Х				
Withdrawal Visit			Х	Х				
Safety Follow-up Visit			Х	Х				

ADA=anti-drug antibody; EOI=End of infusion; PK=pharmacokinetic; CEC=circulating endothelial cell

- ^{a.} Archival tissue collection permitted if tissue was collected within 1 month of completion of last treatment or biopsy if no tissue available.
- ^{b.} May be drawn up to 7 days prior
- ^{c.} May be drawn on day 3 or 4 before LMB-100 administration
- ^{d.} Cycle 2 only. May be obtained on any one of Days 4-8.

C1D1 (within 7 days prior to treatment): optional biopsy.

Note: Timed samples scheduled for EOI must be drawn within 5 minutes of this reference point. Those scheduled within 4hrs of EOI should be collected within +/- 20 minutes of indicated time.

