1.1.3 Exploratory Objectives

- To obtain preliminary assessment of activity including change in appropriate serum tumor markers with treatment, objective response rate (ORR), disease control rate after 3 cycles (~9 weeks) of treatment (DCR), progression free survival (PFS) and overall survival (OS)
- Evaluate association between anti-LMB-100 antibody titer and peak serum drug level
- To examine the relationship between MSLN expression and response to treatment
- To evaluate changes in the tumor microenvironment following treatment with LMB-100 plus tofacitinib
- To assess changes in circulating immune cell and cytokine levels caused by the treatment
- For treatment extension: To determine whether to facitinib can continue to prevent ADA formation beyond 3 cycles of treatment regardless of whether patients had another intervening therapy or not.

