3.2.2.4.1 Additional Precautions for administration of LMB-100 in patients with IRR during LMB-100

Participants receiving LMB-100 who have experienced an IRR of Grade 2 to 4 during a previous infusion despite standard pre-mediation should also receive:

• Dexamethasone 8 mg IV, or equivalent dose of another corticosteroid as clinically indicated

(See Section **3.3.1** for complete instructions on response to IRRs)

Participants who experienced an IRR of Grade 3 or 4 where dexamethasone or another steroid was pre-administered should not receive further LMB-100 and will be discontinued from study therapy.

	Dose (mg)	Route
Acetaminophen	650	РО
Diphenhydramine	25-50	PO or IV
Ranitidine [#]	150	РО
Dexamethasone*	8	IV

[figure not shown]
Table 11. Pre-medications for LMB-100

*Given only in case of prior IRR

[#] IV ranitidine or famotidine 20 mg PO or IV are allowed if the preferred pre-medication is unavailable.

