3.2.3 Schematic view of the administration set-up

3.3 DOSE MODIFICATIONS

3.3.1 LMB-100

LMB-100 infusion may be held for up to 48 hours due to drug-associated toxicity or adverse events from other intercurrent medical conditions (such as primary cancer diagnosis) that resolve with or without medical intervention to grade 1 or less within this time frame. Toxicities for which further LMB-100 treatment should NOT be given are stated below in **Table 12**, which also provides guideline on how to manage some toxicities anticipated with LMB-100.

Event	Action to Be Taken
IRR/hypersensitivity reaction during administration of LMB-100	If an IRR/hypersensitivity develops, the infusion of LMB-100 should be temporarily interrupted. The participant should be monitored until complete resolution of the symptoms and treated as clinically indicated. Treatment or concomitant medication may include IV saline, oxygen, bronchodilators, corticosteroids, and vasopressors depending on the symptoms.
	 If the infusion is interrupted: In the event of IRR CTCAE Grade1, upon resolution of symptoms, the infusion will resume at the rate being used at the time that the IRR occurred In the event of IRR Grade 2 or 3, upon resolution of symptoms, the infusion will resume at one-half the previous rate. In the event of IRR CTCAE Grade 3 or Grade 4 (which may include pulmonary or cardiac events) or an anaphylactic reaction, the infusion should not be restarted, and the participant should receive aggressive treatment Participants experiencing IRR CTCAE Grade 4 or anaphylaxis must be permanently discontinued from study treatment For participants receiving LMB-100 who previously experienced IRR CTCAE ≥ Grade 2, the infusion rate for subsequent LMB-100 infusion should be reduced to one-half of the previous rate and corticosteroids premedication should be given 30 minutes prior to infusion in addition to standard pre-medications: Dexamethasone (20 mg PO 6 -12hrs before infusion or 8
	mg IV, $30 - 90$ min before infusion) or equivalent dose of another corticosteroid as clinically indicated
Capillary leak syndrome (CLS)	In the event of Grade 4 CTCAE capillary leak syndrome (urgent intervention indicated):

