For Grade 1-3 Capillary leak syndrome, the symptoms that make up this syndrome will be recorded separately, instead of classifying them as CLS.	 Vasopressor support (e.g., phenylephrine) if indicated to stabilize blood pressure Administer colloidal solutions (e.g., albumin) if there is a clinically significant, symptomatic and persistent systolic blood pressure drop, urine output significantly declines, or serum albumin falls to 2.5 mg/dL or lower
If the PI determines that the symptoms meet the definition of Grade 4 or 5 CLS, they will be recorded separately and CLS Grade 4 or 5 will also be recorded.	 For pulmonary congestion provide diuretic and/or albumin treatment as appropriate Progressive shortness of breath may require endotracheal intubation or drainage of a pleural effusion For oliguria and /or rising serum creatinine level delay LMB-100 if Grade 3 urine output decrease (<10 mL/hr)

Table 12. Guidelines for Managing LMB-100 Adverse Events

Event	Action to Be Taken			
	• Use dopamine if participant is unresponsive to or unable to tolerate fluids			
	• Manage pericardial effusion as outlined in section on "Inflammatory reactions to serosal membranes" below			
Inflammatory reactions to serosal membranes	 Hydrocortisone (200 mg IV) or a glucocorticoid equivalent as clinically indicated 			
	 o In the event of Grade ≥2 CTCAE pericardial effusion (asymptomatic effusion small to moderate size), consider delaying LMB-100 administration. In the event of Grade ≥3 CTCAE pericardial effusion (effusion with physiologic consequences) permanently discontinue LMB-100 treatment. Consult cardiology service for management recommendations which may include pericardial drainage. 			
	• In the event of pleuritis resulting in mild to severe pleuritic pain, treat with analgesics or steroids as clinically indicated			
	 For participants who have previously experienced pleuritis consider administration of dexamethasone 4 mg, PO bid beginning with first LMB-100 infusion and completing 24 hours after the last LMB-100 infusion of the cycle. (If participant is already receiving corticosteroids at dose and schedule at or above this amount as part of the pre-medication regimen, do not give additional steroids for pleuritis) 			
Dehydration	Encourage participants to maintain oral hydration (~1.5 L/ day)			
Nausea	Ondansetron or another anti-emetic should be available as needed			

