10.4.9 Exploratory Analyses

The following are the intended exploratory analyses focusing on the patients in the expansion cohort:

Disease control rate (DCR) at 9 weeks will be estimated along with a 95% confidence interval. PFS and OS will be estimated by the Kaplan-Meier method, along with 95% confidence intervals. Changes in appropriate tumor markers with treatment (if applicable to patient's tumor type) will be determined and tested for change from baseline using a Wilcoxon signed rank test. Titer of free anti-LMB-100 antibodies at the start of each cycle and following completion of treatment will be obtained and results reported descriptively; the relationship of these values with peak serum drug levels of LMB-100 will be explored. Association of response with tumor MSLN expression will be done by comparing levels between responders and non-responders using an appropriate nonparametric test such as a Cochran-Armitage test or Fisher's exact test. Changes in circulating endothelial cells following immunotoxin treatment, changes in serum cytokines following immunotoxin treatment, and changes in tumor microenvironment following immunotoxin treatment will be reported descriptively, with statistical testing of changes as appropriate. Any statistical tests performed on the exploratory endpoints will have results presented without formal adjustment but interpreted in the context of the number of tests performed. In patients receiving treatment extension, the anti-drug antibodies and peak plasma LMB-100 drug levels will be obtained at each cycle after cycle 3 and reported with descriptive statistics. The levels of these

measures after cycle 3 may be compared descriptively to those in earlier cycles for purposes of evaluating the effect of the agent in this small subset of patients.

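### Day 4 cytokine, endothelial-cell and immune-subset draws from cycle 2 may follow dexamethasone pre-medication, and no analysis identifies those samples

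*Combined protocol and SAP*

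**What the plan says.** **Sampling.** Section 5.2 takes baseline samples before tofacitinib on cycle 1 day 1 (cytokines, immune subsets, gene expression) and before LMB-100 on cycle 1 day 4 (cytokines, CECs, immune subsets). All four assays are drawn again on cycle 1 day 9. For CECs and immune subsets the next draw is day 4 of cycle 2, labelled "C2 only : pre- LMB-100". Cytokines carry the same pre-infusion anchor on day 4 of every cycle from cycle 2. Nothing says whether the draw comes before or after pre-medication.

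**Steroid rules.** Standard pre-medication (Section 3.2.2.4) contains no steroid, although IV dexamethasone is kept available for a severe reaction. Section 3.2.2.4.1 adds a corticosteroid for participants "who have experienced an IRR of Grade 2 to 4 during a previous infusion". Table 12 in Section 3.3.1 gives an oral option, "Dexamethasone (20 mg PO 6 -12hrs before infusion", and an IV option 30 to 90 minutes before.

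**Use of the data.** Section 1.1.3 states the aim as "To assess changes in circulating immune cell and cytokine levels caused by the treatment". Section 5.1.3 compares cytokine levels with baseline. Section 10.4.9 reports, among others, "changes in serum cytokines following immunotoxin treatment" descriptively, with testing where appropriate. It has no flag, exclusion or sensitivity analysis for steroid exposure.

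**The concern.** Section 4.1.2 lists systemic corticosteroids among treatments that may affect the immune system, and exempts those given under the protocol. The plan thus recognises that these drugs can disturb the measured quantities and permits them, but does not account for them in the analysis.

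Exposure is not random. The steroid goes to patients who have already reacted, and Section 12.1.2.1 says cytokine release is thought to be partly responsible for such reactions. In those patients a change from a baseline without reaction-triggered steroid to a later sample may mix three things: study treatment, a tendency to react, and dexamethasone. If the draw is taken after the steroid, no later analysis can recover the value before it.

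**Working it through.** The plan gives no figure to reproduce here. The check sets the steroid windows against the draw windows, then asks how many patients could be affected and what that would do.

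**1. Time from steroid to sample**

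For day 4 from cycle 2, take a draw just before infusion. The gap equals the lead time in Table 12. For cycle 1 day 9 no clock time is given, so assume a draw 18 to 30 hours after the start of the day 8 infusion. The gap is that interval plus the lead time. For rescue steroid, subtract up to 0.5 hours, because the infusion lasts about 30 minutes.

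| Steroid | Day 4, cycle 2 and later | Cycle 1 day 9 |
|---|---|---|
| IV pre-medication, 0.5–1.5 h before | 0.5–1.5 h | 18 + 0.5 = 18.5 h to 30 + 1.5 = 31.5 h |
| Oral pre-medication, 6–12 h before | 6–12 h | 18 + 6 = 24 h to 30 + 12 = 42 h |
| Rescue during day 8 infusion | not applicable | 18 − 0.5 = 17.5 h to 30 h |

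Exposure is closest at day 4. The two steroid passages differ: Section 3.2.2.4.1 lists only an IV dose, while Table 12 lists both routes. Table 12 also ends study treatment after a Grade 4 reaction, while Section 3.2.2.4.1 includes Grade 4 among those who go on with added steroid. These passages need reconciling; the sampling issue arises under either.

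**2. How many patients**

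The documents do not give the rate of Grade 2 or higher reactions, so it is an assumption. In the earlier single-agent study, Table 3 shows one Grade 3 reaction in 13 patients and Table 4 shows reactions of any grade in 4 of 13 (exact 95% CI 9 to 61%). For an expansion cohort of 15:

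- At 1/13: expected 15 × 1/13 = 1.2; P(at least one) = 1 − (12/13)^15 = 0.70.
- At 4/13: expected 15 × 4/13 = 4.6; P(at least one) = 1 − (9/13)^15 = 0.996.

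**3. What that would do**

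This step is illustrative only. Assume 15 patients, no study-drug effect, a steroid-induced fall of 40 to 60% in a marker, and a log-scale SD of change of 0.25 to 0.35. None of these values is in the documents. The average change from steroid alone is the exposed fraction times the fall:

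- At 1/13: 0.077 × 0.40 to 0.60 = 3 to 5%.
- At 4/13: 0.31 × 0.40 to 0.60 = 12 to 18%.

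Simulated rejection rate of a nominal two-sided 5% signed-rank test:

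| Exposed of 15 | Rejection rate |
|---|---|
| 0 | about 5% |
| 1 | about 5% |
| 2 | 7–8% |
| 3 | 10–15% |
| 4 | 16–26% |
| 5 | 24–42% |

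**4. A conflict between sampling sections**

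Section 5.1.6.1 puts the cycle 2 immune-cell draw and the post-treatment gene-expression draw on cycle 2 day 1, before therapy. That is 14 days after day 8 in a 21-day cycle, well clear of pre-medication. Section 5.2 puts them on cycle 2 day 4 and cycle 1 day 9 respectively. Only the Section 5.2 timings are exposed.

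**The case against.** The case for leaving the plan alone has real force.

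- **The test is hypothetical.** Section 10.4.9 names the signed-rank test for tumor markers only. Cytokine and CEC changes are mainly descriptive, and circulating immune subsets and gene expression are not named there. This stands: the rejection rates above show sensitivity and do not describe a planned test.
- **The exposed group may be small.** The 4/13 covers any grade, in a study that gave no routine pre-medication (Section 1.2.8.1). Here everyone is pre-medicated. Reactions are linked to anti-drug antibodies (Section 1.2.6), which mostly appear after cycle 1. This also stands for the first cycle 2 draw. It is weaker for the cycle 3 cytokine draw, where reactions in cycles 1 and 2 both count.
- **Exposure can be sorted out afterwards.** Concomitant drugs go in the eCRF (Section 4.1.2) and draw times are logged (Section 5.3.1). This helps identify exposed samples but cannot restore a pre-steroid value.
- **Dropping exposed samples creates its own bias**, because it removes reactors selectively. This stands, and the fix keeps them in the main summary.

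A reader might also infer that the pleuritis regimen contaminates cycle 1 day 9, since it runs to "completing 24 hours after the last LMB-100 infusion of the cycle". The documents do not support that. The regimen is for patients with earlier pleuritis and begins with the first infusion of a cycle; previous LMB-100 recipients are excluded (Section 2.1.2.16). Pleuritis arising in cycle 1 would bring it in from cycle 2, starting with the infusion that the day 4 draw precedes.

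**Conclusion.** The concern holds in a limited form. A fully compliant day 4 draw from cycle 2 onward can be a post-steroid sample compared with a baseline that precedes reaction-triggered steroid, and nothing in the analysis identifies it. Cycle 1 day 9 is a weaker case, at roughly a day after the day 8 dose.

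The size is uncertain: about 1 to 5 of 15 patients, depending on an unstated Grade 2 or higher rate. With one or two exposed, the distortion of a test is negligible to small. It becomes material only at around four or more, under assumed steroid effects.

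Two stronger readings are tempting. One is that the plan will credit steroid effects to study treatment. That depends on reactions that may be few, and Section 10.4.9 describes changes following treatment, although the objective in Section 1.1.3 is worded causally. The other is that cytokine release would be hidden. The cycle 1 day 4 samples (pre-dose, end of infusion, 4 hours) precede any reaction-triggered pre-medication, and only rescue steroid could reach the later two.

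Primary and secondary endpoints, dose decisions and sample size are unaffected. This is a cheap improvement to exploratory outputs.

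**What to change.** 1. In Section 5.2, define the day 4 cytokine draw (cycle 2 onward) and the cycle 2 day 4 CEC and immune-subset draws as taken before any pre-medication, on day 3 or day 4. Footnote c already allows either day for the antibody sample. The pre-medication condition is needed even on day 3, since an oral dose 6 to 12 hours ahead could fall that evening.
2. Reconcile Section 5.1.6.1 with Section 5.2 on the timing of the immune-cell and gene-expression samples.
3. In Section 10.4.9, keep all samples in the main summary, flag those taken after systemic corticosteroid, and prespecify a sensitivity analysis without them. The flag also covers samples that timing cannot protect, such as cycle 1 day 9 and end-of-infusion cytokines. It needs steroid clock times; Section 4.1.2 requires the drug to be recorded but does not mention the time.

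The cost is slightly less flexible draw timing, a time field for steroid doses if one is not already collected, and one extra table. Item 1 has to be in place before sampling, because a missed pre-steroid draw cannot be recovered. No change to the steroid rules is proposed.
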